## 2. Synopsis

### Study Rationale

Necitumumab (IMC-11F8; LY 3012211; Portrazza®) is a recombinant human monoclonal antibody (mAb) of the immunoglobulin G, subclass 1 (IgG1) that blocks the ligand-binding site of the epidermal growth factor receptor (EGFR). EGFR is detectable in approximately 85% of patients with advanced, metastatic non-small cell lung cancer (NSCLC). Necitumumab has shown signals of antitumor activity in 2 Phase 1 trials when administered as monotherapy in heavily pretreated patients including but not limited to patients with NSCLC. Portrazza has recently been approved in the United States (US) and European Union (EU) for the treatment of adult patients with metastatic squamous NSCLC in combination with gemcitabine and cisplatin. The cetuximab FLEX Phase 3 trial has demonstrated a statistically significant improvement in survival for the combination of an EGFR mAb in combination with chemotherapy in the first-line treatment of patients with advanced metastatic NSCLC.

Abemaciclib, a selective and potent small molecule inhibitor of CDK4/6, prevents cell cycle progression through the G1 restriction point, thus arresting tumor growth. Abemaciclib has shown single-agent antitumor activity in a Phase 1 trial in heavily pretreated patients with NSCLC.

Necitumumab and abemaciclib inhibit tumor progression by different, independent modes of action (cell surface and cell nucleus, respectively), where necitumumab blocks the ligand-binding site of the EGFR and abemaciclib blocks DNA synthesis by prohibiting cell cycle progression from G1- to S-phase.

A xenograft tumor cell-line model has shown an add-on effect of necitumumab to abemaciclib where the combination was more effective when compared to the activity of either drug alone.

The individual toxicity profile from clinical trials with each of the compounds (that is, necitumumab and abemaciclib) suggests that no or only marginal overlapping toxicity is expected. The most common Grade 3 adverse events (AEs; > 5% of patients) for single-agent abemaciclib were leukopenia and neutropenia. For necitumumab single agent, the most frequent AEs reported were skin reactions (in terms of rash) and hypomagnesemia.

Different mode of actions, preclinical data, and the clinical efficacy of necitumumab as well as other EGFR mAbs and abemaciclib in NSCLC provide a rationale for the investigation of necitumumab in combination with abemaciclib in patients with Stage IV NSCLC.

The purpose of this Phase 1b study with an expansion cohort is to explore the safety and preliminary efficacy of necitumumab plus abemaciclib in patients with Stage IV NSCLC who have received no more than 2 lines of chemotherapy of which at least one must be platinum-based.

**Clinical Protocol Synopsis: Study I4X-MC-JFCU**

Name of Investigational Product: Necitumumab (LY3012211) and Abemaciclib (LY2835219)	
Title of Study: A Single-Arm, Multicenter, Phase 1b Study with an Expansion Cohort to Evaluate Safety and Efficacy of Necitumumab in Combination with Abemaciclib in Treatment of Patients with Stage IV Non-Small Cell Lung Cancer (NSCLC)	
Number of Planned Patients: Part A Enrolled: 3 to 18 Part B (Expansion Cohort) Enrolled: 50	Phase of Development: 1b

Length of Study: approximately 21 months  Planned first patient visit: 08 Sep 2015  Planned last patient visit: 19 Jun 2017  Planned interim analyses: first 15 evaluable patients in Part B portion of the study who have completed 2 cycles of study treatment (or otherwise discontinued study treatment) will be analyzed for safety. Interim analyses for efficacy may be performed as needed to aid in the planning of future trials. Patients with squamous and nonsquamous NSCLC who received the recommended abemaciclib dose for Part B in Part A will be taken into account for the interim analyses.
	

Objectives:  The primary objectives of the study are:  Part A: to determine the dose-limiting toxicity (DLT) of abemaciclib at doses up to 200 mg when combined with necitumumab 800 mg, in patients with Stage IV NSCLC as measured by the number of patients with a DLT in Cycle 1.  Part B: to evaluate the efficacy of necitumumab in combination with abemaciclib in terms of progression-free survival (PFS) rate at 3 months in patients with Stage IV NSCLC.
 
The secondary objectives of the study are:  Part A:
 
 
• to investigate the safety profile as assessed by clinical and laboratory significant events of necitumumab in combination with abemaciclib
 
• to determine the objective response rate (ORR)
 
• to determine the pharmacokinetics (PK) of necitumumab and abemaciclib
 
• to determine the immunogenicity of necitumumab
 
 
Part B: to demonstrate the safety, efficacy, and feasibility of necitumumab in combination with abemaciclib at the recommended dose by:
 
 
• determining PFS
 
• determining the ORR and disease control rate (DCR)
 
• estimating overall survival (OS)
 
• investigating the safety profile as assessed by clinical and laboratory significant events of necitumumab in combination with abemaciclib
 
• determining the PK of necitumumab and abemaciclib
 
• determining the immunogenicity of necitumumab
 
 
The exploratory objective is to further evaluate as follows:  Parts A and B: to correlate biomarkers with clinical outcomes, including, but not limited to, KRAS mutation assessment, EGFR protein expression, and/or other biomarkers associated with the disease pathobiology, the cell cycle, EGFR pathway, and/or the mechanism of action of the therapeutic molecules.
	

**Study Design:** This is a single-arm, multicenter Phase 1b study with an expansion cohort to investigate necitumumab in combination with abemaciclib in approximately 70 patients with Stage IV NSCLC (American Joint Committee on Cancer Staging Manual, 7th edition). The study consists of 2 parts:

- Part A: Dose-escalation part with increasing doses of abemaciclib (100 mg, 150 mg, or 200 mg every 12 hours [Q12H] on Days 1 to 21) to determine a recommended dose range for abemaciclib that may be safely administered in combination with a fixed regimen of necitumumab 800 mg Days 1 and 8 every 21 days in patients with Stage IV NSCLC.
- Part B (expansion cohort): Dose confirmation of abemaciclib in combination with a fixed regimen of necitumumab 800 mg on Days 1 and 8 every 21 days and exploration of clinical antitumor activity.

Approximately 50 patients will be enrolled in Part B: approximately 25 patients with squamous histology and approximately 25 patients with nonsquamous histology.

Patients will be treated until progressive disease, toxicity requiring cessation, protocol noncompliance, or withdrawal of consent. Patients who are on study therapy at study completion may continue to receive study therapy in the extension phase until they meet the discontinuation criteria. Study completion is expected to be approximately 5 months after the last patient has been enrolled.

**Diagnosis and Main Criteria for Inclusion and Exclusions:**

Key inclusion/exclusion criteria at the time of enrollment

- The patient has Stage IV NSCLC.  
Part A: NSCLC Stage IV (any type)  
Part B: NSCLC Stage IV (squamous and nonsquamous)
- The patient must have progressed after platinum-based chemotherapy AND have received a maximum of 1 other prior chemotherapy for advanced and/or metastatic disease OR must be judged by the physician as ineligible for further standard second-line chemotherapy. Prior treatment with EGFR-tyrosine kinase inhibitor and anaplastic lymphoma kinase (ALK) inhibitors is mandatory in patients whose tumor has an EGFR activating mutations or ALK translocations. Prior targeting agents and neoadjuvant/adjuvant therapies are permitted with the exception of CDK4/6-targeting agents or necitumumab.
- Measurable disease at the time of study entry as defined by Response Evaluation Criteria In Solid Tumors version 1.1 (RECIST 1.1).
- The patient has tumor tissue available for biomarker analyses.
- The patient has resolution to Common Terminology Criteria for Adverse Events (CTCAE) Grade  $\leq$ 1 of all clinically significant toxic effects of prior chemotherapy, surgery, or radiotherapy (with the exception of alopecia).
- Eastern Cooperative Oncology Group performance status score of 0-1.
- The patient has no brain metastases that are symptomatic.

**Test Product, Dosage, and Mode of Administration:**

- Necitumumab is a sterile, preservative-free, intravenous infusion supplied in 50-mL vials containing 16 mg/mL (800 mg/50 mL) of product, and administered at a dose of 800 mg on Days 1 and 8 of each 21-day cycle.
- Abemaciclib is administered orally as capsules (supplied for clinical trial use in strength of 50 mg/capsule) every 12 hours. In Part A, abemaciclib will be administered at increasing doses of 100, 150, or 200 mg Q12H on Days 1 to 21. In Part B, abemaciclib will be administered at a fixed dose determined in Part A of the study Q12H on Days 1 to 21.

**Reference Therapy, Dose, and Mode of Administration:**

Not Applicable

**Planned Duration of Treatment:**

Baseline period: 21 days

Treatment period: 21 days treatment cycle.

Short-term follow-up (postdiscontinuation): 30 days

Long-term follow-up (postdiscontinuation): begins the day after short-term follow-up is completed and continues until the patient's death or overall study completion

Study Completion: approximately 5 months after the last patient qualified for Part B of the study has enrolled

Study Extension: Patients who are on study therapy at study completion may continue to receive study therapy in the extension phase until they meet the discontinuation criteria.

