**Figure JFCU.8.2. Study period and continued access diagram.**

### 8.1.2. Continued Access Period

The continued access period will apply to this study only if at least 1 patient is still on study treatment when study completion occurs. Patients receiving study treatment and experiencing ongoing clinical benefit and no undue risks may continue to receive study treatment in the continued access period until one of the criteria for discontinuation is met (Section 7.3). Lilly will notify investigators when the continued access period begins.

Patients who are in short-term follow-up when the continued access period begins will continue in short-term follow-up until the 30-day short-term follow-up visit is completed. Long-term follow-up does not apply.

Patients who are in long-term follow-up when the continued access period begins will be discontinued from long-term follow-up.

During the continued access period, all AEs, SAEs, and study drug exposure will be reported on the CRF. Serious adverse events will also be reported to Lilly Global Patient Safety (see Section 10.2.1.1). In the event that an SAE occurs, Lilly may request additional information (such as local laboratory results, concomitant medications, and hospitalizations) in order to

evaluate the reported SAE. Blood samples for PK and immunogenicity analysis will be collected in the event of an infusion-related reaction and during the continued access follow-up.

During the continued access period, the sponsor will collect only the data shown in [Attachment 1](#). It is recommended that routine monitoring, using an assessment schedule similar to that outlined in [Attachment 1](#) (including radiographic evaluation of disease), be continued as necessary to confirm patient eligibility to continue on treatment. However, the results of all these assessments may not be routinely collected by the sponsor, and all nonmandatory assessments (that is, all assessments not explicitly described in [Attachment 1](#)) may be performed locally rather than centrally.

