### **10.1.2. Efficacy Assessments during the Study Period Postdiscontinuation Follow-Up**

Postdiscontinuation follow-up during the study period will be conducted as described in the Study Schedule ([Attachment 1](#)).

For those patients who discontinue study treatment without objectively measured PD, the investigative sites will continue to monitor patients and periodically evaluate tumor response at the same frequency and by the same method used at baseline and throughout the study until the patient has objective disease progression, starts a new anticancer therapy, or until study completion, whichever occurs first. After the patient has objective disease progression or starts a new anticancer therapy, radiologic tests are no longer required and the patient will be followed up approximately every 3 months [ $\pm 7$  days] until the patient's death or overall study completion, whichever comes first.

Response (CR or PR) should be confirmed before the initiation of additional anticancer therapy. However, initiation of new therapy should not be delayed solely to confirm response.

After patients have discontinued study treatment, they may receive additional anticancer therapy at the discretion of the investigator. These postdiscontinuation therapies should be documented on the CRF.

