	10.3.2.3	Plasma sample for Biomarker Analysis	Refer to Attachment 7			
	10.3.2.1	Whole blood for Pharmacogenetic evaluation	Refer to Attachment 7			
	10.2.2.1	ECG (local)	X*			* To be performed every second cycle starting from Cycle 2

Abbreviations: AE = adverse event; Att. = Attachment; CNS = central nervous system; CT = computed tomography; CTCAE = Common Terminology Criteria for Adverse Events; D = Day; ECG = electrocardiogram; DLT = dose-limiting toxicity; ECOG = Eastern Cooperative Oncology Group; IP = investigational product; IRR = infusion-related reaction; MRI = magnetic resonance imaging; PD = progressive disease; PK = pharmacokinetic; RECIST = Response Evaluation Criteria In Solid Tumors; SAEs = serious adverse events.

Postdiscontinuation Follow-up Schedule, I4X-MC-JFCU

Procedure Category	Protocol Section	Procedure	Postdiscontinuation Follow-up		Comments	
			Cycle	Short-Term Follow-up		Long-Term Follow-up
			Visit	801		802-8XX
			Relative day within a cycle			
Physical Examination		Weight	X			
		Blood pressure/pulse	X			
	Att. 4	ECOG performance status	X			
Tumor Assessment	10.1.2	Radiologic imaging (according to RECIST v1.1) and tumor measurement	X	X	Patients who discontinue study treatment for any reason other than PD will continue to undergo radiographic tumor assessments every 6 weeks (±3 days) until PD, the initiation of a new anticancer therapy or overall study completion, whichever occurs first. After the patient has objective disease progression, radiologic tests are no longer required and the patient will be followed up approximately every 3 months (±7 days) until the patient's death or overall study completion, whichever occurs first.	
Survival information	10.1.4	Collection of survival information		X	Collection of survival data every 3 months (±7 days). Whenever possible, survival follow-up is conducted in person. If an in-person visit is not possible, the site may confirm survival by contacting the patient directly via telephone.	
Adverse Events	10.2.1	AE collection and CTCAE grading	X	X	Data on SAEs that occur before the end of trial will be stored in the collection database and the Lilly Safety System. During Postdiscontinuation long-term follow-up, only SAEs that are related to protocol procedures or study treatment will be collected.	
Concomitant Medications	9.5	Concomitant medication notation	X			
Laboratory/Diagnostic Tests	Att. 2	Hematology (central)	X			
	Att. 2	Chemistry (central)	X			

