5.6.2.3. Overall Survival

Overall survival duration is measured from the date of first dose of study drug to the date of death from any cause. For each patient who is not known to have died as of the data-inclusion cut-off date for a particular analysis, OS will be censored for that analysis at the date of last contact prior to the data inclusion cutoff date (contacts considered in the determination of last contact date include adverse event date, lesion assessment date, visit date, and last known alive date).

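### No vital-status check at the data cut-off: overall survival is censored earlier for progressed patients than for others, by up to about 3 months

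*Protocol*

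**What the plan says.** The Protocol synopsis (Planned Duration of Treatment) states: "Long-term follow-up (postdiscontinuation): begins the day after short-term follow-up is completed and continues until the patient's death or overall study completion". The end point is defined there too: "Study Completion: approximately 5 months after the last patient qualified for Part B of the study has enrolled". Section 8.1 places the final analysis at about the same time, so the last patients enrolled have only about 5 months of potential follow-up.

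Contact frequency depends on the patient's status:

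- On treatment: visits on Days 1 and 8 of each 21-day cycle (Attachment 1).
- Off treatment without progression: "Patients who discontinue study treatment for any reason other than PD will continue to undergo radiographic tumor assessments every 6 weeks" (Attachment 1), until progression, new anticancer therapy or study completion.
- After progression or new anticancer therapy: "radiologic tests are no longer required and the patient will be followed up approximately every 3 months" (Protocol 10.1.2). Attachment 1 gives the same interval for survival data, with a window of ±7 days.

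Protocol 8.1.2 then closes follow-up: "Patients who are in long-term follow-up when the continued access period begins will be discontinued from long-term follow-up". The same section lets patients in short-term follow-up complete their 30-day visit, but it asks for no final contact with those in long-term follow-up. The vital-status search in Protocol 7.3.4 covers patients lost to follow-up. Protocol 10.2.1.1 keeps deaths from disease progression out of SAE reporting unless they are possibly drug related.

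Protocol 10.1.4 censors OS at the date last known alive. SAP 5.6.2.3 says "OS will be censored for that analysis at the date of last contact prior to the data inclusion cutoff date", and counts adverse event, lesion assessment, visit and last-known-alive dates as contacts.

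**The concern.** Kaplan-Meier estimation assumes that patients censored at a given time have the same prospects as those still followed. Here the distance between last contact and cut-off is set by progression, which is strongly prognostic for death. Two things can happen, depending on how sites report:

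- Deaths surface only at the next scheduled contact. Deaths in the last interval are then lost, and progressed patients leave the risk set early. OS looks somewhat too good.
- Deaths are reported as they occur, but survivors are not updated. Events are counted while survivors' time at risk is cut short. OS looks too poor.

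Estimating OS is a Part B secondary objective (Protocol 6.2), and SAP 5.6 reports 6-month and 1-year rates. With minimum follow-up of about 5 months, both rates depend on how recently enrolled patients are censored.

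**Working it through.** **The plan's own figures.** The documents give no OS event count, median or precision. Their one design calculation concerns the primary endpoint. With 50 patients and success at 60% or more, the threshold is 0.60 × 50 = 30. Exact binomial: P(X ≥ 30 | 50, 0.50) = 0.1013 and P(X ≥ 30 | 50, 0.65) = 0.8139, matching the stated 0.10 and 81%. Nothing in it uses OS follow-up.

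**Length of the gap.** The interval is 3 × 30.4375 = 91.3 days. With the 7-day window it is 98.3 days, or 3.2 months. If the cut-off falls at random within a 3-month interval, the mean gap is 3/2 = 1.5 months. Allowing for the 30-day visit, the model below gives about 1.0 to 1.5 months. On treatment the longest scheduled gap is 14 days (Day 8 to the next Day 1). Off treatment without progression it is 6 weeks.

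**Example from the schedule alone.** Take a last-enrolled patient dosed on the day of enrollment who progresses at the week 6 scan and stops treatment.

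- The 30-day visit falls at about day 42 + 30 = 72.
- If the 3-month clock starts with long-term follow-up, the next contact is at about day 72 + 91 = 163.
- Study completion is at about day 5 × 30.4375 = 152, before that contact.
- A surviving patient is censored 152 − 72 = 80 days (2.6 months) early.
- If the clock starts at progression instead, the contact is at day 42 + 91 = 133 and the gap is 19 days. The text does not settle which applies.

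**Accrual limit.** From 08 Sep 2015 to 19 Jun 2017 is 650 days, or 21.4 months. Taking the last visit as study completion, 21.4 − 5 = 16.4 months is the most that Parts A and B together can use. Part B's own accrual time is not stated.

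**Share of deaths unseen if found only at contacts.** Assumptions: exponential PFS with a 3-month rate of 50% or 65% (the plan's two hypotheses); 15% of PFS events are deaths; post-progression survival scaled to a median OS of 6, 9 or 12 months; uniform accrual; 5 months minimum follow-up; contacts every 3 weeks to progression, then a 30-day visit, then every 3 months. Each cell gives the share for 50% / 65% 3-month PFS.

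| Accrual | Median OS 6 months | 9 months | 12 months |
|---|---|---|---|
| 8 months | 12.1% / 9.5% | 13.9% / 14.4% | 13.5% / 14.8% |
| 10 months | 10.3% / 8.0% | 12.1% / 12.2% | 12.0% / 13.1% |
| 12 months | 8.7% / 7.0% | 10.6% / 10.7% | 10.9% / 11.6% |
| 16.4 months | 6.4% / 5.2% | 8.2% / 8.3% | 8.8% / 9.1% |

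Per 50 patients this is 2.0 deaths (of 38.8, lowest cell by count) to 4.1 (of 34.0, highest). Other choices of progression and survival gave about 7% to 16%, so the range is approximate.

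**Effect on 1-year OS.** The 10-month rows assume a median time to progression of 3.5 months and the post-progression median shown.

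| Setting | Status known at cut-off | Deaths found only at contacts | Deaths prompt, survivors not updated |
|---|---|---|---|
| 16.4 months, PFS 65%, median OS 6 | 21.3% | 22.5% (+1.2) | 20.6% (−0.7) |
| 16.4 months, PFS 65%, median OS 9 | 35.6% | 36.8% (+1.2) | 34.0% (−1.6) |
| 16.4 months, PFS 65%, median OS 12 | 50.0% | 50.8% (+0.8) | 48.1% (−1.9) |
| 10 months, post-progression 2.5 | 18.5% | 20.6% (+2.1) | 15.0% (−3.5) |
| 10 months, post-progression 4 | 28.3% | 30.0% (+1.7) | 23.2% (−5.1) |

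Over the wider set of assumptions the shift reaches about 6 points too high or about 13 points too low. Median OS moves by +0.1 to +0.2 or 0 to −0.6 months at 16.4 months of accrual, and by up to +0.7 or −1.6 months at 8 months.

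**The case against.** OS is a secondary endpoint with no hypothesis, test or event target, and Protocol 8.2 calls the outcome hypothesis generating only. The shift is mostly small beside sampling error. Ignoring censoring, the standard error of a 1-year rate is √(0.19 × 0.81/50) = 5.5 points at 19% and √(0.28 × 0.72/50) = 6.3 points at 28%, so 95% half-widths are about 11 to 12 points. Every shift in the table above is below one standard error. The two reporting patterns push in opposite directions, so a mixture would partly cancel. When deaths and survivors are both cut at the last contact, the main loss is precision.

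The plan also has helpful provisions. Sites follow the schedule until told that the study is complete (8.1.1), survival may be confirmed by telephone (Attachment 1), and the SAP accepts a last-known-alive date.

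The points on size and status stand, and they keep this a modest matter. They do not close the gap. Nothing prompts sites to obtain a known-alive date at the cut-off. Read literally, the SAP uses only contacts before it, so a call the day after would not extend follow-up. A patient between scheduled contacts is not lost, so 7.3.4 does not apply. Because progression deaths normally bypass SAE reporting, prompt notice cannot be assumed. With fast accrual the shift can exceed one standard error.

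**Conclusion.** The gap is in the text: no vital-status check at the cut-off, 3-monthly contact after progression, and censoring at last contact. OS censoring therefore depends on progression status. The early censoring is at most about 3 months and averages about 1.0 to 1.5 months. The size of the effect rests on assumed accrual and survival: roughly 5% to 15% of deaths unseen with a modest upward shift in 1-year OS, or a downward shift of a few points that grows with fast accrual.

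Three stronger readings are tempting but not supported:

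- A single figure such as 1 in 9 deaths missed. The documents give neither a Part B accrual time nor a median OS, and about 11% arises mainly when accrual takes 10 to 12 months. The shortcut 1 − 2^(−1.5/9) = 10.9% is one patient's risk of dying in an average gap with an assumed 9-month median, not the share of all deaths missed.
- Three months as the typical loss. It is the maximum.
- A bias of known direction. The sign depends on how sites report deaths, which the plan does not fix.

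The primary 3-month PFS analysis, its alpha and its power are not affected. This is a cheap improvement worth making.

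**What to change.** Amend Protocol 8.1.1, 8.1.2 and 10.1.4, the long-term follow-up text of Attachment 1, and SAP 5.6.2.3 together. Changing only some of them would conflict with the end of long-term follow-up at study completion. Suggested wording:

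*Before long-term follow-up is closed, sites confirm vital status as of the data cut-off, by telephone or permitted records search, for every patient not known to have died and not withdrawn from follow-up. The contact may fall within a short, stated window around the cut-off. Deaths up to the cut-off are events. Patients confirmed alive at or after the cut-off are censored at the cut-off. All others are censored at the date last known alive.*

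A records search would extend 7.3.4 beyond lost patients, so its legal and ethical limits, and its exclusion of sponsor personnel from the search, should carry over. Patients who withdrew consent or were discontinued from the study stay outside it (7.3, 7.3.3).

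The cost is one telephone or records check per patient not known to have died. The modelled 18.5 to 40.4 deaths per 50 leave about 10 to 32 survivors, some still on treatment and already known to be alive. In the model the check leaves no death before the cut-off unseen. Sample size, treatment and the primary analysis do not change.
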